1 INTRODUCTION

The purpose of this document is to give details for the statistical analysis of study D5180C00037 supporting the clinical study report (CSR).

The reader is referred to the clinical study protocol (CSP) and the electronic case report form (eCRF) for details of study conduct and data collection.

1.1 Study objectives

Table 1 Objectives and Endpoints

Objectives	Estimand description/Endpoints				
Primary objectives					
To assess the ability of tezepelumab 210 mg subcutaneous (SC) to reduce the prescribed OCS dose (≤ 5 mg/day) without loss of asthma control³ in adult participants with OCS-dependent asthma	 Proportion of participants who discontinued OCS without loss of asthma control^a at Week 28 and Week 52 Proportion of participants who reduced daily prescribed maintenance OCS dose to ≤ 5 mg/day without loss of asthma control^a at Week 28 and Week 52 Population: Adult with OCS-dependent asthma requiring high-dose ICS plus a LABA with or without additional asthma 				
	controller and with at least 1 asthma exacerbation in the prior year who received at least one dose of tezepelumab Intercurrent events: • Treatment discontinuation, change in background therapy (other than OCS): All data are included in the analysis according to treatment policy estimand. • Initiate therapy with another biologic for treatment of asthma: hypothetical strategy; final dose for analysis is defined as last reported OCS dose received by participant with asthma stability verified, achieved prior to initiation of another biologic.				

	Summary measures: Proportion of participants and corresponding 95% CI at Week 28 and Week 52		
Secondary objectives			
To assess the ability of tezepelumab 210 mg SC to prevent asthma exacerbations in adult participants with OCS-dependent asthma while OCS dose reduction	 The AAER over 28 weeks and over 52 weeks Rate of asthma exacerbation associated with hospitalisation or emergency room (ER) visit over 28 weeks and over 52 weeks Rate of asthma exacerbation associated with hospitalisation over 28 weeks and over 52 weeks Proportion of participants who did not experience an exacerbation over 28 weeks and over 52 weeks Proportion of participants who did not experience an exacerbation associated with hospitalisation or ER visit over 28 weeks and 52 weeks Proportion of participants who did not experience an exacerbation associated with hospitalisation over 28 weeks and over 52 weeks 		
To assess the ability of tezepelumab 210 mg SC to allow reduction of the prescribed OCS dose without loss of asthma control ^a	 Proportion of participants with ≥ 50% reduction from baseline in daily maintenance OCS dose at Week 28 and Week 52 Categorised percent reduction from baseline in the daily maintenance OCS dose (categories: ≥ 90% to ≤ 100% reduction, ≥ 75% to < 90% reduction, ≥ 50% to < 75% reduction, > 0% to < 50% reduction, no change or any increase) at Week 28 and Week 52 Absolute and percent change from baseline in daily maintenance OCS dose at Week 28 and Week 52 		
To assess the ability of tezepelumab to improve lung function	Change from baseline in post-BD FEV ₁ at Week 28 and Week 52		

To assess the ability of tezepelumab to improve asthma control ^a	Change from baseline in Asthma Control Questionnaire 6 (ACQ-6) at Week 28 and Week 52
To assess the ability of tezepelumab to improve asthma related quality of life	Change from baseline in standardised Asthma Quality of Life Questionnaire for 12 years and older (AQLQ[s]+12) total score at Week 28 and Week 52
	Change from baseline in St. George's Respiratory Questionnaire (SGRQ) total score at Week 28 and Week 52
Safety objective	
To describe the safety and tolerability of tezepelumab	Serious adverse events (SAEs), discontinuation of investigational product due to an adverse event (DAEs), and adverse events of special interest (AESI)
Exploratory objectives	
To describe changes from baseline in biomarker levels	Change from baseline in biomarker levels at Week 28 and Week 52
To assess the ability of tezepelumab 210 mg SC to allow reduction of the prescribed OCS dose without loss of asthma control ^a	Time to 50% reduction of OCS dose at Week 28 and Week 52
	Time to 100% reduction of OCS dose at Week 28 and Week 52
To describe the occurrence of AI	Proportion of participants with normal, partial, complete AI at Week 28 and Week 52
To assess the ability of tezepelumab to improve asthma control ^a	Proportion of ACQ-6 responders at Week 28 and Week 52
To assess the ability of tezepelumab to improve asthma related quality of life	Proportion of AQLQ(s)+12 responders at Week 28 and Week 52
	Proportion of SGRQ responders at Week 28 and Week 52
To describe the ability of tezepelumab to improve Asthma Impairment and Risk	Change from baseline in AIRQ at Week 52
Questionnaire (AIRQ TM)	• Proportions of AIRQ responders at Week 52

To describe the ability of tezepelumab to improve Sino-nasal Outcome Test (SNOT-22)	Change from baseline in Sino-nasal Outcome Test (SNOT-22) at Week 28 and Week 52
	• Proportion of SNOT-22 responders at Week 28 and Week 52
To describe participant satisfaction with change in daily OCS use	Change from baseline in Participant Perception of OCS (PPOCS) score at Week 28 and Week 52
To evaluate the ability of tezepelumab to reduce exposure to SCS	Mean daily exposure of systemic corticosteroids (mg/day) taken for asthma reasons over 28 and 52 weeks

^a Loss of asthma control is defined as asthma worsening or exacerbation. Asthma worsening is defined by an increase of ACQ-6 score ≥ 0.5 from baseline. Asthma exacerbation is defined by worsening of asthma symptoms that leads to temporary bolus/burst of systemic corticosteroids (or a temporary increase in stable OCS background dose) for at least 3 consecutive days (a single depo-injectable dose of corticosteroids being considered equivalent to a 3-day bolus/burst of systemic corticosteroids), and/or an ER or urgent care visit requiring systemic corticosteroid, and/or inpatient hospitalisation, both due to asthma. ^b The AIRQ questionnaire is not assessed at Week 28 and the objective is analysed at Week 52 only (see Section 2).

1.2 Study design

This is a phase 3b, single-arm, multicentre study in adult participants with severe asthma on high-dose ICS plus LABA and long-term OCS therapy. Participants may be treated with or without additional asthma controller(s). Each participant must have been receiving an average daily OCS dose equivalent to ≥ 5 mg of prednisone/prednisolone for the last 3 months before study entry.

Approximately 300 participants will enter the induction phase. The distribution of participants across the range of screening blood EOS levels are controlled by ensuring that approximately the following ratios are met:

- 80% of participants with blood EOS count at screening $\geq 150 \text{ cells/}\mu\text{L}$
- 10% of participants with blood EOS count at screening < 150 cells/μL and documented history of EOS \geq 300 cells/ μ L within 12 months prior to Visit 1
- 10% of participants with blood EOS count at screening < 150 cells/μL without documented history of EOS \geq 300 cells/ μ L within 12 months prior to Visit 1 (ie, participants with documented EOS < 300 cells/μL over the last 12 months prior to Visit 1, or undocumented history of EOS \geq 300 cells/ μ L within 12 months prior to Visit 1 or unknown EOS counts within 12 months prior to Visit 1).

The study aims at evaluating the efficacy and safety of reducing OCS use after initiation of a 210 mg dose of SC tezepelumab Q4W.

The total duration of the study for each participant is approximately 68 weeks.

Study is divided in 4 periods: screening, induction phase, OCS reduction and maintenance phase, and follow-up as described below and summarized in the Figure 1.

- 1. Screening From Week -4 to Week 0 (up to 4 weeks): Eligibility criteria checked at Visit 1. At Visit 1, participants continue with or be switched to prednisone/prednisolone. Participants who are taking an alternative systemic steroid and not taking prednisone/prednisolone as their OCS treatment are switched to a bioequivalent dose of prednisone/prednisolone (see CSP appendix D). In participants who switched to prednisone/prednisolone, dose has to remain stable for at least 2 weeks before Week 0.
- 2. **Induction phase From Week 0 to 4:** After confirmation of eligibility criteria, participants start receiving tezepelumab treatment at Visit 2/Week 0 and should remain stable on their baseline OCS dose during this phase.
- 3. Oral corticosteroid reduction and maintenance phase From Week 4 to Week 52: Site visits occur Q4W. Participants reduce their dosage of OCS according to the schema defined in the CSP Table 7 for each baseline OCS dose until they reach the lowest stable OCS dose or until Week 48. The first OCS dose reduction may occur at Visit 3. OCS dose reduction may occur remotely if the scheduled dose reduction does not coincide with a site visit.

Participants are considered as having reached the lowest stable dose when they have discontinued OCS or no further OCS reduction is possible because of loss of asthma control and/or evidence of AI (as confirmed by morning cortisol test or adrenocorticotropic hormone [ACTH] stimulation test).

Once they reach the lowest stable dose, participants are considered in maintenance period. From Week 48 to Week 52, all participants remain on their stable daily OCS dose, except if an asthma deterioration or exacerbation occurs. No further down-titration are allowed from Week 48 onwards.

The evaluation of the HPA axis integrity starts for all participants who have been on 5 mg/day OCS. A screening method with morning serum cortisol is done to evaluate whether the participant has normal cortisol levels or complete AI. Cortisol levels from the morning cortisol test below normal range and above the complete AI range are considered 'indeterminate' and will require additional testing (ACTH stimulation test or alternative method). Further details are provided in the CSP Section 8.2.1 and CSP Appendix M).

At each visit, in addition to the participant's asthma symptoms, investigators use the participant's weekly ACQ-6 scores (completed by the participant at home by means of a handheld electronic participant-reported outcome device [ePRO]), and further reduce the OCS dose unless asthma control is lost (deterioration or exacerbation as described below) or AI prevents further dose reduction.

[figure not shown]
Asthma deterioration is defined by an increase of ACQ-6 score \geq 0.5 from baseline. Asthma exacerbation is defined by worsening of asthma symptoms that leads to:

- A temporary bolus/burst of systemic corticosteroids (or a temporary increase in stable OCS background dose) for at least 3 consecutive days to treat symptoms of asthma worsening; a single depo-injectable dose of corticosteroids will be considered equivalent to a 3-day bolus/burst of systemic corticosteroids.
- Or, an ER or urgent care visit (defined as evaluation and treatment for <24 hours in an emergency department or in an urgent care centre) due to asthma that required systemic corticosteroids (as per the above).
- Or, an in-patient hospitalisation (defined as admission to an inpatient facility and/or evaluation and treatment in a healthcare facility for ≥ 24 hours) due to asthma.

After recovery from the first exacerbation or asthma deterioration, the participant is allowed to proceed with another attempt to reduce OCS dose; however, this must follow a lower speed of OCS down-titration. In case of a second exacerbation or asthma deterioration, no further OCS dose reduction is allowed, and the participant continues the same OCS dose or return to a one-step higher dose level (or more as considered necessary by the investigator). The new OCS dose established after a second asthma exacerbation or deterioration is maintained until Week 52. Further details are provided in the CSP.

4. **Follow-up (Week 64):** A follow-up contact (phone call) is scheduled at Week 64 or 16 weeks (± 5 days) after the last dose of tezepelumab.

Figure 1 Study Design flow chart

All participants who prematurely discontinue tezepelumab or discontinue from the study should return to the study site and complete the procedures described for the premature IPD visit within 4 weeks (\pm 7 days) after the last dose of tezepelumab. In addition, participants who prematurely discontinue tezepelumab are encouraged to remain in the study and complete all subsequent scheduled study visits, procedures, and assessments through study completion (more details in CSP Section 7.1).

1.3 Sample size justification

The sample size for this study is based on the ability to provide sufficient precision in point estimates, both in the Full Analysis Set (FAS) and subsets for statistical analysis.

The primary outcomes variables, the proportion of participants who have discontinued OCS without loss of asthma control and the proportion of participants who reduced OCS dose to ≤ 5 mg/day without loss of asthma control. For the sample size estimation, a success rate of 50% is assumed. Estimate precision is expressed in a two-sided 95% CI distance from the point estimate of a 50% success rate to confidence limit for a total of approximately 300 participants. Calculations were conducted using the exact Clopper-Pearson CI formula for a single proportion in R v.4.0.1 (function *binom.test()* from *stats* package).

A total sample size of approximately 300 participants entering the induction phase was expected to provide 95% CIs for a single proportion extending approximately 5.8% from the point estimate of a 50% success rate. Estimates of the 95% CI of a > 50% success rate are incrementally smaller, as is shown in Table 2.

Table 2 Expected Distance Between Observed Proportion and Confidence Limit (Clopper-Pearson 95% CI Width)

Proportion of participants	Sample size					
	50	100	150	200	250	300
50	± 14.5	± 10.25	± 8.3	± 7.1	± 6.4	± 5.8
60	-14.8 +13.6	-10.3 +9.7	-8.3 +7.9	-7.1 +6.8	-6.4 +6.1	-5.8 +5.6
70	-14.6 +12.1	-10.0 +8.8	-8.0 +7.2	-6.9 +6.3	-6.1 +5.6	-5.5 +5.1
80	-13.7 +10.0	-9.2 +7.3	-7.3 +6.1	-6.2 +5.3	-5.5 +4.8	-5.0 +4.4

The table also shows that the 95% CIs for subpopulation analyses as small as 50 are < 15% for proportions between 50% and 80%.

Note: The planned interim analysis does not impact the sample size calculation.

2 CHANGES TO PROTOCOL PLANNED ANALYSES

No difference with the most recent version of the CSP.

3 DATA ANALYSIS CONSIDERATIONS

3.1 Timing of Analyses

There are 2 database locks (DBLs). The primary DBL carried out after approximately 300 participants completed 28 weeks. All data available at that time is part of the DBL and is analysed with the main focus on estimates of a subset of the pre-planned analysis outputs at Week 28. The final DBL conducted once the last participant completed the safety follow-up visit (Week 64) with the main focus on estimates on Week 52 (end of treatment [EOT]).

An interim analysis (IA) may also be performed as described in Section 5.

3.2 Analysis Populations

3.2.1 All Participants Analysis Set

Comprises all participants screened for the study and used for reporting of disposition and screening failures.

3.2.2 Full Analysis Set

Includes all enrolled participants who received at least one dose of tezepelumab, irrespective of their protocol adherence and continued participation in the study. Participants are analysed irrespective of whether they prematurely discontinue, according to the intent-to-treat principle. Participants who withdraw from the study are included up to the date of their study termination.

All efficacy, demographics, baseline characteristics, and safety analyses are performed using the FAS.

3.2.3 Currently or Historically Elevated EOS Population

Includes participants who received at least one dose of tezepelumab and with peripheral blood EOS count of ≥ 150 cells/ μ L assessed by central laboratory at Visit 1 or documented EOS count of ≥ 300 cells/ μ L in the past 12 months. Participants are analysed irrespective of whether they prematurely discontinue, according to the intent-to-treat principle. Participants who withdraw from the study are included up to the date of their study termination.

Primary efficacy analyses, key demographics and baseline characteristics are also presented using the currently or historically elevated EOS population in addition to the FAS as described in Section 3.2.2.

3.3 General Considerations

In general, continuous endpoints are summarised using the mean, the standard deviation, median, minimum value, and maximum value, and the categorical endpoints are summarised using frequency counts and percentages, as well as a two-sided 95% CI for proportions computed using exact Clopper-Pearson method. Time to event data is presented graphically using Kaplan Meyer curve.

Absolute change from baseline is defined as (post-baseline value – baseline value). The percent change from baseline is defined as {(post-baseline value – baseline value)/baseline value)}*100. Baseline calculations are defined in the Section 3.3.1.2.

For participants' proportion calculation, the denominator is the number of participants in the Full Analysis Set defined in Section 4.1.2 unless otherwise stated.

No imputation performed beyond the approach defined for outcome measures. Imputation for partial date is detailed in the Appendix A.

Unless specified otherwise, the daily maintenance OCS dose, including the daily OCS at baseline (Section 3.3.1.2) and the final daily OCS dose (Section 4.2.1.2), is defined based on the prescribed maintenance dose of OCS, expressed as a dose per day, at the time of the relevant visit. If a participant is on a fixed daily dose, then the OCS dose is defined as that prescribed dose. If the participant is on every other day regimen (or different doses every other day), then the OCS dose is defined as the average amount prescribed to be taken each day. For example, should a participant be on a 10 mg every other day regimen of OCS, their OCS dose is defined as 5 mg.

Maintenance dose of OCS is collected on the ECSYSCRT eCRF page with a therapy reason of "Asthma maintenance dose", "Titration, due to asthma", "AI based on cortisol test", "Signs/symptoms of AI" and "Adrenal crisis". If the maintenance OCS doses with more than one therapy reasons (including only those mentioned earlier) are prescribed on the same day (e.g., "Asthma maintenance dose" and in addition "Signs/symptoms of AI"), then the sum of the doses are calculated.

Note that the prescribed OCS dose with therapy reason of "Asthma exacerbation per protocol" or "Worsening of asthma, without exacerbation" is not included in the daily OCS dose calculation. In case of overlapping OCS doses taken for asthma worsening or exacerbation with maintenance doses of OCS, the latter one is excluded from the daily OCS dose calculation.

The statistical analyses for this study are conducted using SAS® v9.4 or latest version in a secure and validated area.

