9.4.3 Efficacy

9.4.3.1 Primary Endpoints

The following outcomes are designed to support the primary objective of the study:

- Proportion of participants who discontinue OCS without loss of asthma control
- Proportion of participants who reduce OCS dose to ≤ 5 mg/day without loss of asthma control

The baseline OCS dose is defined in Section 9.4.1. The final OCS dose is defined based on the prescribed maintenance dose, expressed as a dose per day, at Week 28 or Week 52. If the participant is on a fixed daily dose, then the OCS dose is defined as that prescribed dose. If the participant is on every other day regimen, then the OCS dose is defined as the average amount prescribed to be taken each day. Final daily OCS dose will be derived as described in Table 13. Further details may be specified in the SAP.

Table 13 Final Daily Maintenance OCS Derivation

Situation	Final daily maintenance OCS dose
Initiation of therapy with another biologic for treatment of asthma	Last reported OCS dose ^a received by participant with asthma stability verified ^b prior to initiation of another biologic.
Premature withdrawal from the study	Last reported OCS dose ^a received by participant with asthma stability verified ^b at the time of study withdrawal.
Any other situation	Last reported OCS dose ^a received by participant with asthma stability verified ^b

^a daily OCS dose is based on information collected in ECSYSCRT eCRF.

Each primary endpoint will be summarised by number and proportion (with 95% CI) of participants. The 95% CIs for proportions will be calculated using the Clopper-Pearson exact method.

Analysis of the primary endpoints will be based on both the FAS population and the current or historical elevated EOS population. In addition, primary endpoints will be summarised by pre-specified subgroups using FAS population including (but not limited to):

- Baseline EOS group: $< 300/\mu L$, $\ge 300/\mu L$
- Baseline EOS group: $< 150/\mu L, \ge 150/\mu L$.

Any further requirements for subgroups analysis and exact definition of all relevant categories where needed, will be pre-specified in the SAP.

^b Asthma stability is defined as no change in OCS dose for at least 2 weeks.

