The same visit window definitions are used regardless of whether the planned treatment period or the on-treatment period is used for analysis. Each data record in the planned treatment period is first identified, and then further flagged as on-treatment if applicable. This flag is used to select all eligible records for subsequent visit windowing, according to whether the derived visits are to be used in a planned treatment period or an on-treatment period analysis. It should be noted that, if treatment was discontinued within a particular visit window, the rules above for handling two values within the same visit window could select a different record according to whether a planned treatment period analysis or an on-treatment period analysis is needed.

Table 3 summarises the visit windows to be used. "4-weekly Visit Window" corresponds to the 4-weekly protocol scheduling for clinic visits, including those variables which are not captured at every clinic visit, unless otherwise stated. Sparse visit windows are defined also for specific parameters not measured every 4 weeks.

The 4-weekly visit window approach is replaced by a weekly based approach for ACQ-6 measured weekly. For Week 1, the window is [2; 11] and then for each week, the window is defined as (Target day for Week X - 3; Target day for Week X + 3), where Target day for Week X = (Week number * 7) + 1. For example: Target day for Week 10 is 71 (i.e., 10*7+1) and the visit window is (68 - 74).

Visit windows presented in Table 3 does not apply for calculation of daily OCS dose at each timepoint. The OCS dose at each visit is based on actual visit dates to account for changes in OCS dose at scheduled visit. The visit window at Week X is calculated as [Visit(X-1) date + 2 days; Visit(X) date + 1 day]. For Week 52, the visit window is [Visit 14 date + 2 days; Visit 15 date].

Table 3. Adjusted analysis Visit Windowing

Visit	Time	Target	4-weekly Visit	Spar	Sparse Visit Window			
	Point	Day	Window	(Sparse CSP sch		edule)		
				AQLQ	SGRQ/ PPOCS/ SNOT-22	AIRQ		
Visit 2	Week 0	1	NA	NA	NA	NA		
Visit 3	Week 4	29	2 - 42	2-56	-	-		
Visit 4	Week 8	57	43 - 70			-		
Visit 5	Week 12	85	71 - 98	-	-	-		
Visit 6	Week 16	113	99 - 126	-	-	-		
Visit 7	Week 20	141	127 - 154	-	-	-		
Visit 8	Week 24	169	155 - 182	-	-	-		
Visit 9	Week 28	197	183 - 210	169-224	169-224	-		
Visit 10	Week 32	225	211 - 238	-	-	-		
Visit 11	Week 36	253	239 - 266	-	-	-		
Visit 12	Week 40	281	267 - 294	-	-	-		

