4.2.1.3 Handling of Dropouts and Missing Data

No data imputation for the primary endpoint.

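### SAP 3.3 excludes both the exacerbation/worsening dose and the overlapping maintenance dose, so read literally no OCS dose counts on overlap days, contrary to its own definition and protocol 9.4.3.1

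*SAP*

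**What the plan says.** SAP 3.3 defines the daily maintenance OCS dose, at baseline and as the final dose, as one that "is defined based on the prescribed maintenance dose of OCS, expressed as a dose per day, at the time of the relevant visit". It lists the therapy reasons that count as maintenance. OCS recorded for a protocol exacerbation, or for worsening without exacerbation, "is not included in the daily OCS dose calculation". The next sentence deals with overlap: "In case of overlapping OCS doses taken for asthma worsening or exacerbation with maintenance doses of OCS, the latter one is excluded" from the same calculation.

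Protocol 9.4.3.1 has no such exclusion: "The final OCS dose is defined based on the prescribed maintenance dose, expressed as a dose per day, at Week 28 or Week 52". It derives the value through Table 13 (last reported dose unchanged for at least 2 weeks) and allows the SAP to add detail. SAP 2 reports: "No difference with the most recent version of the CSP".

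On missing values, SAP 3.3 says "No imputation performed beyond the approach defined for outcome measures" and SAP 4.2.1.3 says "No data imputation for the primary endpoint". SAP 4.2.7.3 and 4.2.13.3 also rule out imputation.

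**The concern.** In the overlap sentence the second item named is the maintenance dose, and the exacerbation dose has already been removed one sentence earlier. Both records therefore drop out, and neither document says what value the day then takes. Programmers acting in good faith could code it as missing, as 0 mg, or as the maintenance dose.

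The derivation is shared. It feeds the final dose (both primary endpoints, the ≥ 50% reduction and the categorised reduction), the by-visit dose in 4.2.7, the interim dose in 4.2.1.8, and time to 50% and 100% reduction in 4.2.13. Overlap is foreseeable: the exacerbation definition includes a temporary rise in the stable background dose, and the SAP sentence itself anticipates overlap.

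**Working it through.** **Step 1: apply the two sentences.** Take a day with assumed records of 5 mg maintenance and 40 mg for an exacerbation. The first sentence removes the 40 mg and the second removes the 5 mg, so nothing countable remains. The section's own definition and protocol 9.4.3.1 both give 5 mg.

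**Step 2: what value does the empty day take?** The no-imputation statements favour missing. So does the look-back: "The visit window at Week X is calculated as [Visit(X-1) date + 2 days; Visit(X) date + 1 day", with the latest dose in the window taken (4.2.7.2), and Table 4 uses the last reported dose. This does not settle the matter, because the documents do not show how a true 0 mg is recorded. If discontinuation appears as the absence of a maintenance record, an excluded day looks the same.

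**Step 3: worked cases.** Inputs:
- Visit 8 on day 169 and Visit 9 on day 197 (target days, SAP Table 3).
- OCS window for Week 28: 169 + 2 = 171 to 197 + 1 = 198, which is 28 days.
- Final dose: last dose unchanged for at least 14 days, looking back from day 197 (Table 4).
- Doses and course dates are assumed.

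Case 1: 10 mg throughout, course on days 193–199. Case 2: 10 mg throughout, course on days 184–197. Case 3: 7.5 mg (held at least 14 days) reduced to 5 mg on day 180, course on days 186–192.

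| Case | Output | Maintenance kept | Overlap missing | Overlap 0 mg |
|---|---|---|---|---|
| 1 | By-visit dose | 10 mg | 10 mg (from day 192) | 0 mg |
| 1 | Final dose | 10 mg | 10 mg | 10 mg |
| 1 | First 50% and 100% date | none | none | day 193 |
| 2 | By-visit dose | 10 mg | 10 mg | 10 mg (day 198 follows the course) |
| 2 | Final dose | 10 mg | 10 mg | 0 mg |
| 2 | First 50% and 100% date | none | none | day 184 |
| 3 | Final dose | 5 mg | 7.5 mg if the run is broken, 5 mg if bridged | 7.5 mg |
| 3 | First 100% date | none | none | day 186 |

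Case 3 arithmetic: with maintenance kept, 5 mg runs 197 − 180 + 1 = 18 days, so it is stable. If excluded days break the run, the two pieces are 185 − 180 + 1 = 6 days and 197 − 193 + 1 = 5 days. Neither reaches 14, so the final dose falls back to 7.5 mg and the participant is no longer a ≤ 5 mg responder. The SAP does not say which applies.

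**Step 4: when could 0 mg coding give a false discontinuation?** The course must supply 14 days at 0 mg, with fewer than 14 days of resumed maintenance by day 197. For a course ending on day e this means 197 − e < 14, so e ≥ 184: a course of 14 days or more ending on any of days 184–197. Time to reduction is more exposed, because 4.2.13.2 takes the first day on which the threshold is met and sets no stability condition. For by-visit values, 4.2.7.2 also refers to 4.2.1.2, so the stability rule may limit a false 0 mg there. Under the missing reading, a course must cover all 28 window days to leave no by-visit value.

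**Step 5: scale.** The plan's precision figure reproduces: exact 95% limits for 150 of 300 lie 5.80 points either side, against the stated 5.8. One reclassified participant moves a proportion by 1/300 = 0.33 points. The documents give no number of overlapping courses, so the total cannot be computed.

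**The case against.** Four arguments carry weight.

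- **Little happens on the favoured reading.** In Cases 1 and 2, missing and maintenance kept give identical results. This stands for a participant on a steady dose, but Case 3 shows that it does not extend to one who has just tapered.
- **The protocol allows SAP detail and itself works through the last stable dose.** It is true that the final dose is not simply the dose on the visit day. But removing the prescribed maintenance dose takes away the quantity being defined rather than adding detail, so the conflict remains and SAP 2 does not declare it.
- **The rule may be deliberate.** Withholding stability credit while control is lost fits endpoints that require no loss of asthma control. A reader might infer that the sentence is plainly a slip; the documents do not settle intent. Even if it is deliberate, the SAP does not state the aim, the value for the day, or whether the run is broken, and a conservative result depends on that last point.
- **Overlap depends on data entry.** A temporary increase might replace the maintenance record instead of running beside it, and the form's completion rules are not shown. This stands, and it is one reason why no size can be given.

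**Conclusion.** The wording defect is certain: as written, no dose counts on overlap days, against the section's own definition and protocol 9.4.3.1. Its effect on results is unknown. Under the missing reading it is usually nil, with a possible change in ≤ 5 mg status after a recent taper. Under 0 mg coding, false reduction dates and, less readily, a false discontinuation are possible. It should be fixed because the rule is wrong in a derivation shared by the maintenance-OCS endpoints, not because a large shift in the primary result is expected.

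Three stronger readings are not supported. A reader might infer that the primary discontinuation rate is inflated; that needs 0 mg coding, which the text does not favour, together with a long course close to the visit. A reader might infer that affected participants have no dose at all; only the overlap days are empty, and the look-back normally finds an earlier value. A reader might also size the problem from the one prior-year exacerbation required for entry; that is a minimum, it leaves out courses for worsening alone, and it gives no bound for this trial.

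**What to change.** Replace the overlap sentence in SAP 3.3 with:

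> Where OCS recorded for asthma worsening or exacerbation overlaps a maintenance OCS record, the worsening/exacerbation dose is excluded and the prescribed maintenance dose is used. An excluded record is never itself read as 0 mg; the daily dose is 0 mg only where the prescribed maintenance dose is 0 mg (OCS discontinued), including during a course given after discontinuation.

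The last clause protects participants already off OCS, whose maintenance dose really is 0 mg during a later course.

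Under Table 4, add one sentence stating whether a worsening or exacerbation course interrupts the 2-week stability run. It should agree with the no-loss-of-control condition in the endpoint (SAP Table 1 footnote a and 4.2.1.1), so that keeping the maintenance dose does not by itself make a participant in or just after a course count as stable. If withholding stability credit was the purpose of the present sentence, this is the place to say so.

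Cost: one sentence replaced, one added, and a programming check. No new data are needed.
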